11.3 Response Criteria for MF

Response categories	Required criteria (for all response categories, benefit must last for ≥12 weeks in order to qualify as a response)
Complete Remission (CR)	Bone marrow: * Age-adjusted normocellularity; <5% blasts; ≤Grade 1 myelofibrosis**, AND Peripheral blood: Hemoglobin ≥100 g/L and <UNL; Neutrophil count ≥1 x 10 ⁹ /L and <UNL; Platelet count ≥100 x 10 ⁹ /L and <UNL; <2% immature myeloid cells***, AND Clinical: Resolution of disease symptoms; Spleen and liver not palpable; No evidence of EMH
Partial Remission (PR)	Peripheral blood: Hemoglobin ≥100 g/L and <UNL; Neutrophil count ≥1 x 10 ⁹ /L and <UNL; Platelet count ≥100 x 10 ⁹ /L and <UNL; <2% immature myeloid cells***, AND Clinical: Resolution of disease symptoms; Spleen and liver not palpable; No evidence of EMH OR Bone marrow: * Age-adjusted normocellularity; <5% blasts; ≤Grade 1 myelofibrosis**, AND Peripheral blood: Hemoglobin ≥85 but <100 g/L and <UNL; Neutrophil count ≥1 x 10 ⁹ /L and <UNL; Platelet count ≥50 but <100 x 10 ⁹ /L and <UNL; <2% immature myeloid cells***, AND Clinical: Resolution of disease symptoms; Spleen and liver not palpable; No evidence of EMH
Clinical improvement (CI)	The achievement of anemia, spleen or symptoms response without progressive disease or increase in severity of anemia, thrombocytopenia or neutropenia‡
Anemia response	Transfusion-independent patients: a ≥20 g/L increase in hemoglobin level† Transfusion-dependent patients: becoming transfusion-independent††
Spleen response§	A baseline splenomegaly that is palpable at 5-10 cm, below the LCM, becomes not palpable§§, OR A baseline splenomegaly that is palpable at >10 cm, below the LCM, decreases by ≥50%§§ A baseline splenomegaly that is palpable at <5 cm, below the LCM, is not eligible for spleen response Confirmation by MRI or CT showing ≥35% spleen volume reduction is recommended (but not required)
Progressive disease¥	Appearance of a new splenomegaly that is palpable at least 5 cm below the LCM, OR A ≥100% increase in palpable distance, below LCM, for baseline splenomegaly of 5 to 10 cm, OR A 50% increase in palpable distance, below LCM, for baseline splenomegaly of >10 cm, OR Leukemic transformation confirmed by a bone marrow blast count of ≥20%, OR A peripheral blood blast content of ≥20% associated with an absolute blast count of ≥1 x 10 ⁹ /L that lasts for at least two weeks
Stable	Belonging to none of the above listed response categories

disease	
Relapse	No longer meeting criteria for at least CI after achieving CR, PR or CI, OR Loss of anemia response persisting for at least one month, OR Loss of spleen response persisting for at least one month

Key: UNL, upper normal limit; LCM, left costal margin; MRI, magnetic resonance imaging; CT, computed tomography; EMH, extramedullary hematopoiesis (no evidence of EMH implies the absence of pathology- or imaging study-proven non-hepatosplenic EMH) ;

*Baseline and post-treatment bone marrow slides are to be stained at the same time and interpreted at one sitting by a central review process. Cytogenetic and molecular responses are not required for CR assignment.

**Grading of myelofibrosis is according to the European classification (*Thiele et al. Haematologica 2005;90:1128*) . It is underscored that the consensus definition of “a complete remission bone marrow” is to be used only in those patients where all other criteria, including resolution of leukoerythroblastosis, are met. It should also be noted that it was a particularly difficult task for the working group to reach a consensus regarding what represents a complete histological remission.

***Immature myeloid cells constitute blasts + promyelocytes + myelocytes + metamyelocytes + nucleated red blood cells. In splenectomized patients, <5% immature myeloid cells is allowed.

‡See table for definitions of anemia response, spleen response and progressive disease. Increase in severity of anemia constitutes the occurrence of new transfusion dependency or a ≥ 20 g/L decrease in hemoglobin level from pre-treatment baseline that lasts for at least 12 weeks. Increase in severity of thrombocytopenia or neutropenia is defined as a 2-grade decline, from pre-treatment baseline, in platelet count or absolute neutrophil count, according to Common Terminology Criteria for Adverse Events (CTCAE) version 5.0. In addition, assignment to clinical improvement (CI) requires a minimum platelet count of $\geq 25,000 \times 10(9)/L$ and absolute neutrophil count of $\geq 0.5 \times 10(9)/L$

†Applicable only to patients with baseline hemoglobin of <100 g/L. In patients not meeting the strict criteria for transfusion-dependency at the time of study enrollment (see below), but have received transfusions within the previous month, the pre-transfusion hemoglobin level should be used as the baseline

††Transfusion dependency before study enrollment is defined as transfusions of at least 6 units of packed red blood cells (PRBC), in the 12 weeks prior to study enrollment, for a hemoglobin level of <85 g/L, in the absence of bleeding or treatment-induced anemia. In addition, the most recent transfusion episode must have occurred in the 28 days prior to study enrollment. Response in transfusion dependent patients requires absence of any PRBC transfusions during any consecutive “rolling” 12-week interval during the treatment phase, capped by a hemoglobin level of ≥ 85 g/L.

§In splenectomized patients, palpable hepatomegaly is substituted with the same measurement strategy

§§Confirmation of spleen or liver responses by imaging studies is recommended (but not required), where a $\geq 35\%$ reduction in spleen volume, as assessed by magnetic resonance imaging (MRI) or computed tomography (CT), is required. Furthermore, a $\geq 35\%$ volume reduction in the spleen or liver, by MRI or CT, constitutes a response regardless of what is reported with physical examination.

¶Symptoms are evaluated by the Myeloproliferative Neoplasm Symptom Assessment Form total symptom score (MPN-SAF TSS).¹⁷ The MPN-SAF TSS is assessed by the patients themselves and includes fatigue, concentration, early satiety, inactivity, night sweats, itching, bone pain, abdominal discomfort, weight loss, and fevers. Scoring is from 0 (absent/as

good as it can be) to 10 (worst imaginable/as bad as it can be) for each item. The MPN-SAF TSS is the summation of all the individual scores (0-to-100 scale). Symptoms response requires $\geq 50\%$ reduction in the MPN-SAF TSS.

Confirmation by MRI or CT is recommended (but not required) to confirm progressive disease assignment for splenomegaly, where a $\geq 25\%$ increase in spleen volume from baseline is required for confirmation. Baseline values for both physical examination and imaging studies refer to pre-treatment baseline and not to post-treatment measurements.

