2.0 Goals

2.1 Primary Goals

- 2.11 To estimate the clinical efficacy of AZD1775 in combination with AraC in patients with newly diagnosed AML by assessing complete response (CR plus CRi) rates
- 2.12 To estimate the clinical efficacy of AZD1775 alone or in combination with AraC in patients with relapsed/refractory AML and hypomethylating agent failure MDS by assessing complete response (CR plus CRi) rates
- 2.13 To evaluate the clinical efficacy (best overall response including clinical improvement) of AZD1775 in patients with advanced MF defined as intermediate and high risk MF (primary or secondary MF)

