Blood and Lymphatic System Disorders	Febrile neutropenia \geq Grade 3	AZD1775	May omit dose until fever has resolved or returned to baseline. Dose to be restarted at same dose level or treating physician may discuss possible dose reduction (per Table 8.12) with the Study Chair. If clinical benefit is derived, AZD1775 may be continued if the infection is managed and controlled with appropriate medical intervention (i.e. antibiotics) and the patient is felt to derive benefit from the treatment with AZD1775 (Rationale: AML, MDS and MF patients may have persistent and/ or prolonged neutropenia and will only recover if underlying disease is adequately treated].

→ → Use the NCI Common Terminology Criteria for Adverse Events (CTCAE) version 5.0* unless otherwise specified ← ←			
CTCAE System/Organ/Class (SOC)	ADVERSE EVENT	AGENT	ACTION**
Investigations	Neutrophil & Platelet count decrease ≥ grade 4 NOTE: only applicable for patients with absolute neutrophil count (ANC) of ≥ 1000mm ³ and platelet count ≥ 100,000/mm ³ at baseline (i.e. MDS or MF patients)	AZD1775	Omit dose until ANC and/or platelets have recovered to ≤ grade 2. If clinical benefit is derived, AZD1775 may be continued if not recovered to ≤ grade 2 after discussion of treating physician and study chair. For a second event reduce by 1 dose level (Table 8.12) For a third event discontinue from treatment. [If clinical benefit is derived, AZD1775 may be continued per physician assessment and after discussion with Study Chair and Medical Monitor (NYU DSMC)]
Investigations	Creatinine increased Grade 2	AZD1775	Omit dose until resolved to ≤ grade 1, then: 
 • If resolved in ≤ 7 days, then maintain dose level • If resolved in > 7 days, then decrease by 1 dose level (Table 8.12) [If clinical benefit is derived, AZD1775 may be continued if the renal function is elevated but stable]
		AraC	Continue treatment at current dose level
	Creatinine increased Grade 3 and 4	AZD1775	Omit dose until resolved to ≤ grade 1, then decrease dose by 1 dose level
		AraC	Omit dose until resolved to ≤ grade 1, then decrease dose by 1 dose level
Investigations	Blood bilirubin increased ≥ Grade 3	AZD1775	Omit dose until resolved to ≤ grade 1, then: 
 • If resolved in ≤ 7 days, then maintain dose level • If resolved in > 7 days, then decrease by 1 dose level
		AraC	Continue treatment at next lower dose level

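### The platelet floor for clinical improvement in MF carries the wrong unit (about 1,000-fold too high), so read literally no MF patient can be assigned that response

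*Combined protocol and SAP*

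**What the plan says.** Section 2.1 lists, as goal 2.13: "To evaluate the clinical efficacy (best overall response including clinical improvement) of AZD1775 in patients with advanced MF". CI is the only response category that this goal names.

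The table in Section 11.3 defines CI as "The achievement of anemia, spleen or symptoms response without progressive disease", and without worsening of anemia, thrombocytopenia or neutropenia. A footnote attached to that row defines worsening and then sets two count floors: "In addition, assignment to clinical improvement (CI) requires a minimum platelet count of" 25,000 x 10⁹/L or more, and neutrophils of 0.5 x 10⁹/L or more. Both are mandatory.

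The same table gives the platelet limits for the better responses:

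- CR and the first PR route: "Platelet count ≥100 x 10"⁹/L, and below the upper normal limit.
- Second PR route: "Platelet count ≥50 but <100 x 10"⁹/L.

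Relapse in the same table includes the loss of at least CI status after CR, PR or CI. The CI floor is stated nowhere else in the protocol, so nothing corrects it.

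**The concern.** CI is the least demanding of the three MF response categories, yet its platelet floor lies far above the floors for CR and PR. CR also requires platelets below the upper normal limit, so no realistic count could meet both the CR range and the CI floor. An ordering of responses in which the lowest category needs the highest count cannot be what was meant.

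CI is also where a signal is most likely in this cohort. CR and every PR route require resolved symptoms, a spleen and liver that cannot be felt, and strict blood limits. Section 1.1 puts response rates on current therapies in advanced MF below 5-10%. With seven patients (Sections 6.0 and 16.1), a rule that removes CI removes most of what the cohort could show. It also affects relapse coding: a patient who drops from CR or PR to what should count as CI would, read literally, be recorded as relapsed.

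**Working it through.** The plan gives a threshold here and no derived figure, so there is nothing to reproduce. The check is a unit conversion and a comparison with the plan's own limits.

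**Inputs**

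| Quantity | Value | Source |
|---|---|---|
| CI platelet floor as printed | 25,000 x 10⁹/L | 11.3, CI footnote |
| CI neutrophil floor | 0.5 x 10⁹/L | same sentence |
| CR platelet and neutrophil floors | 100 and 1 x 10⁹/L | 11.3 table |
| Second PR route, platelet and neutrophil floors | 50 and 1 x 10⁹/L | 11.3 table |
| Platelet count written per mm³ | "platelet count ≥ 100,000/mm"³ | Table 8.32 |
| MF cohort | 7 patients | 6.0, 16.1 |

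**1. Convert the printed floor.** One litre is 10⁶ mm³, so 25,000 x 10⁹ / 10⁶ = 25,000,000 per mm³.

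**2. Compare it with the table's own floors.**

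- Against CR: 25,000 / 100 = 250 times.
- Against the second PR route: 25,000 / 50 = 500 times.

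**3. Compare it with possible counts.** The documents give no numerical upper normal limit, so these ranges are assumptions.

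- Upper normal limit of 350 to 450 x 10⁹/L: 25,000 / 350 = 71 and 25,000 / 450 = 56, so the floor is 56 to 71 times normal.
- Extreme thrombocytosis of 1,000 to 3,000 x 10⁹/L: 25,000 / 1,000 = 25 and 25,000 / 3,000 = 8.3, so the floor is still 8 to 25 times higher.

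**4. Find the likely source of the slip.** Table 8.32 writes platelets per mm³, and 100,000 per mm³ = 100 x 10⁹/L. By the same conversion 25,000 per mm³ = 25 x 10⁹/L, and 25,000 / 25 = 1,000. A floor of 25 x 10⁹/L lies below the PR floor (50) and the CR floor (100), as a lesser category should.

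**5. Check it against the neutrophil floor.** The ratio of platelet floor to neutrophil floor is 100 / 1 = 100 for CR and 50 / 1 = 50 for the second PR route. For CI it is 25,000 / 0.5 = 50,000 as printed, and 25 / 0.5 = 50 after correction.

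**6. Effect on the cohort.** As printed, the probability of CI is 0 for each patient, so the count is 0 of 7. If CI were attainable at a true rate p, the chance of at least one CI is 1 - (1 - p)⁷. The documents give no p, so a range is shown.

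| Assumed p | Chance of at least one CI in 7 |
|---|---|
| 0.05 | 0.30 |
| 0.10 | 0.52 |
| 0.20 | 0.79 |
| 0.30 | 0.92 |

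**The case against.** The case for treating this as a trivial slip has five parts.

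- **A reader would notice.** The value is visibly absurd, the neutrophil floor beside it is on the right scale, and the plan describes no programmed derivation of CI. This is fair, and it makes actual misclassification less likely. But Section 11.3 is the protocol's own MF definition, and coding should not depend on each assessor silently correcting it.
- **Only the CI label is blocked.** CR and PR have workable platelet limits, and anemia, spleen and symptom responses can be reported separately. This stands, and the finding is limited accordingly.
- **No decision rests on it.** The primary endpoint in Section 16.21 is CR plus CRi. Section 6.37d1 keeps MF patients out of the Arm C analysis and summarizes them descriptively. Alpha, power and arm selection are untouched. This also stands, and it limits the severity.
- **The intended value is inferred.** The floor appears once, and the criteria behind it cannot be checked from the documents. This stands: the sponsor has to confirm the number.
- **The exponent could be a misreading of the page.** A multiplier of 10⁶ per litre would make the value right, since 25,000 x 10⁶/L = 25 x 10⁹/L. The neutrophil floor in the same sentence uses the same notation and makes sense, so this is unlikely. A look at the source page would settle it.

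**Conclusion.** The point holds. As written, the CI floor is 25 million platelets per mm³, which is 250 times the CR floor and 500 times the second PR floor in the same table. Read literally, no MF patient can reach the CI part of goal 2.13, and the relapse definition inherits the fault. The internal contradiction rests on the protocol's text alone. The claim that no patient could reach the floor assumes platelet counts no higher than 3,000 x 10⁹/L, and the 1,000-fold size assumes that 25 x 10⁹/L was meant.

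The consequence is bounded: one response category in a seven-patient descriptive cohort, with CR, PR and the decision rules for the three main arms unaffected. It should be corrected because the category is named in a primary goal, and because reinterpreting the threshold after responses are known would be post hoc.

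**What to change.** Restate the CI platelet floor in Section 11.3 in the unit used by the rest of the table. The reading that fits the table is 25 x 10⁹/L, which is 25,000 per mm³; the sponsor should confirm it against the response criteria that the table was taken from. Leave the neutrophil floor of 0.5 x 10⁹/L as it is, and check that the MF response and relapse coding uses the corrected value.

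The cost is one unit in one footnote, with no change to sample size, visits or data collection. If any MF responses have already been assigned, review the CI and relapse entries once against the corrected floor and record that this was done.

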11.4. Symptom Assessment Package for MF

Given there is no currently validated instrument of patient-reported outcomes (PRO) for serial administration in patients with ET or PV to be used in a clinical trial setting we have adopted a standard validation approach used for new PRO instruments. The new PRO instrument to be tested (MPN-SAF) and a well validated questionnaire for assessing health related quality of life will be given to patients at baseline and prior to treatment on cycles 3, 6, and 9, and at study discontinuation. The symptom assessment package of instruments will be completed by enrolled patients on-site at the time of their study visits.

MPN-SAF: The MPN-SAF (Appendix IV) was created to address the constellation of symptoms most frequent in MPN patients based on the results of our internet based survey of 1179 MPN patients ((PV (N=405); ET (N=304); MF (N=456))(2). Our survey demonstrated that the vast majority of the MPN patients have very significant fatigue compared to age matched published data. Given the central importance of this symptom, and need for accurate measurement on a trial, the previously validated Brief Fatigue Inventory (BFI) is included as item 1-9 (3), and a composite score is generated for the BFI (the score is the mean result of all 9 items). Items 10-13 address spleen related symptoms (early satiety, abdominal pain), inactivity, and cough. Items 14-18 address the central MPN symptoms of night sweats, pruritus, bone pain, fever, and weight loss. Although some of these symptoms are more frequent in PMF, they are still present in significant numbers of ET and PV patients and are of relevance in this trial given the high risk patients included on study will also include those who already have mild features of post ET/PV MF respectively. Item 19 includes a single item overall quality of life measure. Items 10-16 and 19 are measured on a linear analog scale assessments (LASA). The LASA methodology has proven very valid in the past (4). Additionally, the lack of a composite score overall for the MPN-SAF is a positive attribute for this instrument for serial assessment in a clinical trial for MPN patients as individual symptoms may respond (or worsen) independently with therapy.

The MPN-SAF has previously been validated for use at a single time point(5) by co-administration with previously validated instruments. Measurement of individual symptoms which existed on other validated instruments was highly correlated with single item results on the MPN-SAF. Additionally, patient anonymous feedback demonstrated the MPN-SAF was easy to understand. Additionally patients were questioned to respond to any major symptoms which were not included in the MPN-SAF, and no symptom was mentioned by more than one patient demonstrating the relatively comprehensive nature of the instrument for MPN patients.

EORTC-QLQ C30 (Appendix V): The EORTC-QLQ-C30 version 3.0 (6) is included as our main instrument for co-validation on these trials, and redundant capture of information for impact of protocol therapy on patient's symptoms, mood, and quality of life. The initial EORTC QLQ-C36 questionnaire, later shortened and validated with 30 questions, has the following advantages namely being a) cancer specific b) multidimensional in structure c) appropriate for self-administration d) applicable across a range of cultural settings. This instrument has been thoroughly validated for serial use in cancer clinical trial setting. This instrument although highly valid for a portion of the symptom changes we wish to capture with this trial, never-the-less is not as comprehensive for MPN.

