Bone marrow biopsy and aspirate procedure (cytogenetics or FISH ⁹)	X ⁶			X ³	X ³	X ⁷
Blood specimens (see Section 14.0) ^R	X ^{4,13}		X ⁴	X ⁴	X ⁴	X ⁴
Saliva Sample (see Section 14.0) ^R	X					
Bone marrow aspirate research specimens (see Section 14.0) ^R	X ^{6, 13}			X ⁵	X ⁵	X ⁵
Patient Questionnaire Booklets ⁸	X		X ⁸	X ⁸	X ⁸	X
ECG (12 lead) ¹¹		X	X	X	X	X

1. For women of childbearing potential only Day 1 of each cycle
2. 30 days (+/-3days) post last dose of study drug
3. Marrow biopsies only to be done at End of cycle 2, End of cycle 4, at time of suspected CR/CRi and thereafter at physician discretion as clinically indicated (i.e. disease progression).

4. Blood specimens for research sampling to be collected as defined in Section 14.
 5. Research marrow samples (aspirates) to be done at times of clinical standard of care marrow tests at End of cycle 2, End of cycle 4, at time of suspected CR/CRi or disease progression and thereafter at physician discretion as clinically indicated. A sample will be obtained at end of study (EOS) if a bone marrow is performed as part of patient's standard of care; sample will be collected per section 14.0
 6. ≤ 28 days prior to registration; for patients with an outside marrow biopsy within 8 weeks of study start, outside results can serve as baseline after review at NYU.
 7. Bone marrow at end of study is only to be done at physician discretion and is optional. Progression marrow can be used as EOS marrow if patient is taken off trial based on the results.
 8. Patient questionnaire booklet must be used; copies are not acceptable for this submission. Booklet should be completed by patient prior to review of treatment response and discussions of patient's general health since last treatment evaluation. Booklets to be completed at end of all cycles.
 9. Either conventional cytogenetics or FISH panel (or both based on physician discretion) for MDS should be performed at baseline. If diploid cytogenetics at baseline subsequent cytogenetic studies may be omitted unless disease progression is suspected. For FISH based cytogenetic assessments, an entire MDS FISH panel should be performed at baseline, while on subsequent marrows only positive specific FISH abnormalities/probes need to be repeated unless disease progression is suspected.
 10. Prior to the start of treatment.
 11. ECG in triplicate on day1 of each cycle. NOTE: for cycle 1, ECGs will be conducted at least weekly.

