- 16.5 Exploratory Analysis
- An exploratory analysis will be conducted, if there is indication, to determine any differences in study endpoints for subgroups of patients within each treatment arm as defined by the grouping factors (section 5.0), descriptive factors (section 12.0), dose level or any other patient demographics.
- 16.6 Correlative Research
- 16.61 Statistical analysis of pharmacokinetics and biomarkers will be primarily descriptive. Continuous biomarker levels will be explored in a graphical manner

including mean plots and plots of change and percent change from baseline and other summary measures. Any potential relationships between the baseline level or change in the level of each biomarker and clinical outcome such as overall response, 6-month progression and survival, and adverse event incidence will be further analyzed using Wilcoxon rank sum tests or logistic regression methods, as appropriate. Association between a dichotomized biomarker and overall response will be assessed using a chi-squared test. Comparisons with 1-sided p-values ≤ 0.10 are considered significant. As this correlative component is exploratory in nature, we have not adjusted for multiple comparisons.

- 16.62 Patient-reported outcomes will be assessed at baseline, cycles 3, 6, 9, and EOS.. MPN-SAF TSS was created to address the constellation of symptoms. The MPN-SAF includes 1 item measuring fatigue from the previously validated Brief Fatigue Inventory (BFI), as well as linear analog scales capturing early satiety, abdominal discomfort, inactivity, concentration problems, numbness/tingling in the hands/feet, night sweats, itching, bone pain, fever, and weight loss. The MPN-SAF TSS has previously been validated for use at a single time point by co-administration with previously validated instruments.

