Quality of life will be assessed prior to review of treatment response and discussions of patient's general health since last treatment evaluation. QOL will be measured using the EORTC QLQ-C30, a 30-item patient-reported questionnaire about patient ability to function, symptoms related to the cancer and its treatment, overall health and quality of life, and perceived financial impact of the cancer and its treatment. 28 of the 30 items are measured on a 1-4 scale (1=not at all; 4=very much) with the remaining two items (overall health and overall quality of life) scored on a 1-7 numeric analogue scale (1=very poor; 7=excellent). The recall period for the EORTC QLQ-C30 is one week. The EORTC QLQ-C30 is the product of more than a decade of collaborative research and to date, more than 2200 studies using the EORTC QLQ-C30 have been registered with the EORTC (Fayers et al, 2001 [EORTC Scoring Manual]). The patient booklet containing this questionnaire will be administered to all willing patients via a paper booklet in clinic at baseline and on day 1 of every cycle starting with Cycle 2, and will be scored according to the published scoring algorithms.

Scale score trajectories over time and changes from baseline over time will be examined using repeated measures or growth curve models, as appropriate, stream plots and mean plots with standard deviation error bars overall. Scores and changes at each cycle will be statistically tested using paired t-tests, and standardized response means (i.e. effect sizes) (mean of the change from baseline scores at a given cycle, divided by the standard deviation of the change scores) will be interpreted (after applying Middel's (2002) adjustment) using Cohen's (1988) cut-offs: <0.20 = trivial; 0.20 - <0.50 = small; 0.50 - <0.80 = moderate; and ≥ 0.80 = large.

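### The sparse MPN-SAF schedule in 11.4 and 16.62 conflicts with Table 4.3 and, at 21-day cycles, is too widely spaced to show a 12-week MF symptom response promptly

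*Combined protocol and SAP*

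**What the plan says.** **What counts as a response.** Goal 2.13 for MF is best overall response, including clinical improvement. The table in 11.3 defines clinical improvement as "The achievement of anemia, spleen or symptoms response without progressive disease" and without worsening cytopenias. For every MF response category, "benefit must last for ≥12 weeks in order to qualify as a response". The table notes add: "Symptoms are evaluated by the Myeloproliferative Neoplasm Symptom Assessment Form total symptom score (MPN-SAF TSS"), with a reduction of at least 50% required.

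**When the form is given.**
- Section 11.4: the MPN-SAF and the QLQ-C30 "will be given to patients at baseline and prior to treatment on cycles 3, 6, and 9, and at study discontinuation".
- Section 16.62, opening: "Patient-reported outcomes will be assessed at baseline, cycles 3, 6, 9, and EOS".
- Table 4.3 (MF schedule), footnote 8: "Booklets to be completed at end of all cycles". The table marks the booklet at baseline, in cycles 1, 2 and 3 onwards, and at EOS.
- Section 16.62, later: the booklet containing the QLQ-C30 is given "in clinic at baseline and on day 1 of every cycle starting with Cycle 2".

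**Cycle length.** MF patients receive the Arm C single agent (5.2, 6.37d1), which repeats every 21 days (7.31, 7.32). The Schema gives a 28-day cycle, and Table 4.3 has Day 28 visits in cycles 1 and 2.

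**The concern.** A duration requirement can be met only if the instrument is given often enough, and for long enough, to show it. The symptom route depends entirely on a form that patients complete at fixed visits. The documents disagree on whether those visits come every cycle or every third cycle. If a site follows 11.4 and 16.62 at 21-day cycles, two consecutive on-treatment forms are 9 weeks apart and cannot span 12.

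Two patients with the same symptom course could then be classified differently because their sites followed different sections. The cohort has seven patients, so one reclassification moves the MF response rate by 1/7, about 14 percentage points. Section 1.1 puts median survival in advanced MF at under 6-12 months, so some patients may not reach the cycle 9 form.

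**Working it through.** The plan gives no figure to reproduce; this is calendar arithmetic.

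**Inputs.** Required duration: 12 weeks = 84 days (11.3). Cycle length L: 21 days (7.31, 7.32) or 28 days (Schema). Visit window: ±3 days (Table 4.3). EOS: 30 ± 3 days after the last dose (Table 4.3, footnote 2). Last dose in a cycle: day 12 (7.31).

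**Assumption.** The documents do not say how the 12 weeks are to be shown. I take it to need two forms at least 84 days apart, both showing the 50% reduction.

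**Formulas.** In days elapsed from cycle 1 day 1, cycle c starts at (c − 1) × L and ends at c × L.

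| | L = 21 | L = 28 |
|---|---|---|
| C3 start | 2 × 21 = 42 (week 6) | 2 × 28 = 56 (week 8) |
| C6 start | 5 × 21 = 105 (week 15) | 5 × 28 = 140 (week 20) |
| C9 start | 8 × 21 = 168 (week 24) | 8 × 28 = 224 (week 32) |
| C3 to C6 | 63 days | 84 days |
| C3 to C9 | 126 days | 168 days |
| First on-treatment pair ≥ 84 days, sparse schedule | C3 and C9, week 24 | C3 and C6, week 20 |
| First pair ≥ 84 days, end of every cycle | C1 and C5: 105 − 21 = 84, week 15 | C1 and C4: 112 − 28 = 84, week 16 |

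**Visit windows, L = 21.** The longest C3-to-C6 interval is 63 + 3 + 3 = 69 days, still short of 84. Treatment delays would have to add 84 − 63 = 21 days between the two visits. At L = 28 the interval is exactly 84, with no margin for an early C6 visit.

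**First seen at C6, L = 21.** C6 to C9 is 168 − 105 = 63 days. C9 is the last on-treatment form listed, so this response cannot be confirmed by C9. Only a later discontinuation form could confirm it.

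**Discontinuation/EOS form, L = 21.** If the last dosing cycle is c, EOS falls at (c − 1) × 21 + 11 + 30. Measured from C3 (day 42):
- stop after cycle 5: 125 − 42 = 83 days (80 to 86 with the EOS window), borderline;
- stop after cycle 6: 146 − 42 = 104 days, sufficient;
- stop after cycle 7: 167 − 42 = 125 days, sufficient.

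All three fall before C9 at day 168.

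**Difference between the schedules, L = 21.** On treatment, the earliest confirmation differs by 24 − 15 = 9 weeks.

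**The case against.** The strongest reply is that the needed data are already scheduled. Table 4.3 is the visit schedule for MF patients and asks for the booklet every cycle, so a site that follows it loses nothing. The cycle 3/6/9 wording of 16.62 matches the MDS schedule (Table 4.2, footnote 8) and sits under correlative research. On this view the problem is a text inconsistency in a descriptive pilot cohort. That largely stands and limits the weight of the point. It does not remove it: 11.4 is the MF-specific section on this instrument and gives the sparse visits, and Table 4.3 never names the MPN-SAF. Reading its booklet as including that form rests on the title of Appendix VIII, which pairs the two questionnaires, and on 11.4, which gives both at the same visits.

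A reader might infer three stronger claims that the documents do not support.
- *Twelve weeks can never be shown before cycle 9.* The discontinuation/EOS form can supply the interval for patients who stop after cycle 6 or 7, and long treatment delays could too.
- *Late-enrolled MF patients cannot be confirmed by the time of analysis.* The 4-month minimum observation in 16.3 concerns the primary endpoint, which 16.21 defines as CR plus CRi. MF patients are summarised separately (6.37d1), no MF data cut-off is given, and section 11.0 sets no limit on cycles.
- *The MPN-SAF has three incompatible schedules.* The day-1 wording in 16.62 describes the booklet containing the QLQ-C30, and day 1 of the next cycle is essentially the end of the previous one. In practice two schedules compete: every cycle, and every third cycle.

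**Conclusion.** The point holds as an internal inconsistency that affects one component of the MF goal. At 21-day cycles the schedule in 11.4 and the opening of 16.62 delays the earliest on-treatment confirmation of a symptom response to week 24, against week 15 under Table 4.3. It also leaves a response first seen at cycle 6 unconfirmed at cycle 9. The size depends on nominal visit timing and on the 21-day cycle. At 28 days the cycle 3 and 6 forms just span 84 days, and the schedules differ by 20 − 16 = 4 weeks. The documents support both cycle lengths, so the duration problem cannot be settled until those passages are reconciled.

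The reach is limited. The MF cohort has seven patients and no formal test. Anemia and spleen responses do not use the questionnaire. The part of CR and PR that requires disease symptoms to resolve is affected only if it is judged by this form. The correction is worth making because it costs almost nothing and removes a dependence of the MF response count on which section a site follows.

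**What to change.** 1. Change 11.4 and the opening of 16.62, for MF patients, to the every-cycle schedule in Table 4.3: baseline, end of each cycle (or, equivalently, day 1 of the next cycle before treatment), and EOS. Choose one of the two timings and use it in all three places, including the later booklet sentence in 16.62.
2. Name the MPN-SAF explicitly in the questionnaire row or footnote 8 of Table 4.3.
3. State in 11.3 that the 12-week duration of a symptom response is judged in days: at least 84 days from the first form showing the 50% reduction. Say which later forms must still show it and how a missed form is handled.
4. Reconcile the MF cycle length across the Schema, section 7.3 and the Day 28 visits in Table 4.3. This review takes no position on which is right.

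The cost is wording in an amendment. Table 4.3 already asks for the booklet every cycle, so patient burden does not rise above that table.
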